## **Background**

LCPD is a juvenile hip disease which affects children between 2 and 12 years of age. It is most commonly seen boys at the age around 5-6 years. The aetiology is still unknown. The pathophysiological key event is a partial or complete disruption of the blood supply to the femoral epiphysis. The epiphyseal cartilage, the secondary ossification centre and the metaphysis undergo subsequent changes due to partial or complete osteonecrosis. In the active stages of the disease the femoral epiphysis may deform due to altered mechanical properties. At time of healing the femoral head shape may vary compared to a normal hip. Depending on the residual deformity the patients may have symptoms and complaints even after time of healing and the hip function may be impaired in young adulthood. Such a hip may also predispose for early hip osteoarthritis.

Since symptoms and hip changes are not only restricted to the active phases of the disease, it is mandatory to follow up the patients over a longer period. This study elucidates the hip function, the residual deformity and the patients reported outcome 20 years after the diagnosis with LCPD:

## **Unsolved issues with LCPD**

LCPD has been described for more than 100 years ago(8-10). However, there is no clear consensus on the epidemiology, aetiology the prognostic factors and treatment.

The treatment has changed dramatically in Norway over the last decades. Until the late 70s, children had been treated with traction and weight relief over several months in the active stages. Later, containment treatment was introduced and several orthotic devices had been introduced in order to maintain hip containment. Surgical Containment gained increasing popularity from the late 80s until today.

There is no consensus which treatment gives the most favourable outcomes. Several studies have been published and the results concerning the surgical (7, 11-13) or non-surgical treatment is very divergent (14-16). Most of the studies are retrospective and have a short follow up time. Those studies therefore fail to evaluate the hip shape at time of healing. The main endpoints of most of the studies are based on radiographs, leaving the functional aspect unrecognized. Thus, little is known about patient's hip function, quality of life and treatment satisfaction.

## **Purpose of the study**

The purpose of the study is to evaluate long term outcomes, risk factors and patient reported outcomes in young adults, 20 years after LCPD.

## **Material and methods**

From January 1996 until December 2000 all new diagnosed children with LCPD were registered in a nationwide Perthes study. It is a prospective, multicentre study involving 28 hospitals throughout Norway. The diagnosis was established by the local

orthopedic surgeon based on radiographic findings and clinical diagnostic. All radiographs were reviewed by [name], [name] or [name]. A total of 425 children with LCPD were involved in the study.

The study will follow up all 425 patients and it is structured in 3 phases.

**Phase 1: Follow-up of all patients in the South-Eastern Norway Regional Health Authority (HSØ)**

208 patients with LCPD have been registered in HSØ(163 males and 45 females). Average age at diagnosis was 5.8 years (1.3 – 15.2).

**Phase 2: Follow-up of all patients in the Western and Central Norway Regional Health Authorities (HVOM)**

187 patients with LCPD have been registered in these two regions (141 males and 46 females). Age at diagnosis was 5.7 years (1.7 – 13.5). 93 were treated with physiotherapy, 82 were treated with surgery and 11 patients with orthosis.

**Phase 3: Follow-up of all patients in the North Norway Regional Health Authorities (HN)**

27 patients with LCPD have been registered in this region (18 boys and 9 girls). Age at diagnosis was 6.1 years (1.8 – 13.1). 11 patients were treated with physiotherapy and 16 with orthosis.

Demographics and clinical information have been reported of all 425 patients at the initial visit. Radiographs at diagnosis, 1 year and 5 years follow-up were collected. The extent of the femoral head necrosis was evaluated with the Catterall and lateral pillar classification (17, 18). At 5 years follow-up the residual deformity was classified with the modified Stulberg's classification

The present study is planning to invite all 425 patients to a clinical and radiographic examination. The project starts in 2019 with a pilot study where 20 randomised patients will be examined.

The main study will proceed with the phases as described above. The examination will comprise a clinical visit with functional testing of the hip and radiographs of both hips.

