***Endpoints (primary /secondary)***

Clinical endpoints will be the hip function and quality of life reported by the patients, using the Hip disability and Osteoarthritis Outcome Score (HOOS) (20). There will also be included functional and activity related aspects of a greater population based study in Oslo (21). Furthermore, length leg discrepancies, muscle impairment and Hip impingement tests will be performed.

HOOS: Validated PROM.40 questions to evaluate hip symptoms, hip function on different activity levels and quality of life.

«Oslo population study»: Scientific population study in Oslo to evaluate cardiac risks (21).

If patients would like to participate in the study, but fail to meet up for the visit, a short telephone interview will be performed including a short HOOS\_PS form.

Radiological endpoints

- a.) Stulberg classification
- b.) Coverage of the femoral head (CE angle)
- c.) Osteoarthritis - Jacobsen et al.(22)
- d.) Alterations of the proximal femur (ATD, CCD)
- e.) Total hip replacement.

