## **Significance**

The Norwegian Perthes study is unique in the world. It is the world largest prospective study on Perthes disease. Other long term studies on LCPD are retrospective and they do not investigate the hip function. A variety of different classifications have been used, which makes a direct comparison impossible. No study has been using PROMS in the patient assessment. The present study will be the largest prospective study on this field. It elucidates both radiographic and clinical aspects 20 years after the diagnosis. The results may therefore have a significant impact on a better understanding and the future treatment of LCPD.

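### Does naming the modified Stulberg classification at 5 years, but only the Stulberg classification at 20 years, put hip shape on two different scales?

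*Protocol*

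**What the plan says.** The 5-year grading is described in Material and methods, in the text that follows the Phase 3 description: "At 5 years follow-up the residual deformity was classified with the modified Stulberg's classification". The same paragraph says of the earlier films: "Radiographs at diagnosis, 1 year and 5 years follow-up were collected".

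For the 20-year visit, the section Endpoints (primary /secondary) gives a lettered list of radiological endpoints, of which the first is "a.) Stulberg classification". The word 'modified' is absent. Neither place lists the classes, describes the modification or cites a source for the version.

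On aims, Purpose of the study states: "The purpose of the study is to evaluate long term outcomes, risk factors and patient reported outcomes in young adults, 20 years after LCPD". Background puts it similarly: "This study elucidates the hip function, the residual deformity and the patients reported outcome 20 years after the diagnosis with LCPD".

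**The concern.** Residual deformity is the construct graded at 5 years, and it is named again in Background as something the study will describe at 20 years. One construct in one cohort therefore carries two scale names, with no statement that they are equivalent and no mapping between them. For the Catterall and lateral pillar classifications, HOOS and the osteoarthritis grading, the Protocol cites a source. For Stulberg it cites none at either mention, so a reader cannot look up which version is meant.

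If the two versions draw class boundaries differently, a table of 5-year against 20-year class would mix true change with change of definition. A hip could appear to have remodelled or deteriorated only because the scale changed. The Protocol recognises this kind of hazard when, in Significance, it says of other long-term studies: "A variety of different classifications have been used, which makes a direct comparison impossible". Background also justifies long follow-up by arguing that hip changes continue beyond the active disease, which makes a comparison of the two time points a natural one to want.

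**Working it through.** No sample size, power or error rate in the Protocol depends on this point, so there is no stated figure to reproduce. The check is a reading of the relevant places side by side, followed by a look at what an illustrative size would require.

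**1. Are two scales specified?** The 5-year text names the modified version. The endpoint list gives a bare label. The other entries in that list are equally terse: an angle, abbreviations for proximal femoral measures, joint replacement. An unqualified name in such a list may be shorthand for the version already in use in this cohort, or it may mean the unmodified scale. The text does not decide between them. That is an ambiguity, not a contradiction.

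**2. Is a change in class analysed?** Purpose of the study and Background both describe status 20 years after diagnosis, together with risk factors. The endpoint section lists endpoints assessed at that visit. No objective, endpoint or analysis in the Protocol compares the 5-year class with the 20-year class. The Protocol also does not say that the 5-year visit coincides with healing, so describing the comparison as change since healing has no textual support.

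**3. Which uses of the 5-year class need a common scale?**

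| Use | Stated in the Protocol? | Needs the same version at both times? |
|---|---|---|
| 20-year class as a status endpoint | Yes | No |
| 5-year class as a risk factor for a 20-year outcome (class, CE angle, osteoarthritis, HOOS) | Within the general risk-factor aim | No; predictor and outcome may be on different scales |
| 5-year class tabulated directly against 20-year class | No | Yes |

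Only the last row is exposed, and it is not planned.

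**4. Could a later comparison be rescued?** Films were collected at 5 years, and the 20-year visit includes radiographs of both hips. Nothing in the Protocol prevents both sets being graded on one version.

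**5. How large could the effect be?** Suppose, purely for illustration, that 5% to 15% of patients (one affected hip each) changed class through definition alone. The three regional counts sum to 208 + 187 + 27 = 422, which gives 0.05 × 422 = 21.1 and 0.15 × 422 = 63.3, or about 21 to 63 patients. This range carries no weight, for three reasons.

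- The percentages are not in the Protocol and cannot be derived from it. If the label is shorthand, the proportion is 0% and the count is 0.
- The denominator assumes that every registered patient has both a 5-year and a 20-year grading. The endpoint section provides for a telephone interview when a willing patient does not attend, and such a patient contributes no 20-year film. The title of the first listed reference mentions 368 patients with five-year follow-up. On that count the same assumed percentages give 0.05 × 368 = 18.4 and 0.15 × 368 = 55.2.
- The 422 is itself a sum of regional counts; the Protocol gives the cohort as 425.

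**The case for a change.** The strongest case for a change is that the instrument defining an endpoint belongs in the endpoint section, that naming it costs a few words, and that the Protocol itself criticises mixed classifications elsewhere. Films are also read over several years, through a pilot and three phases with separate data analyses, so an unnamed version might be applied differently from one phase to the next. Regrading old films would cost far more than fixing the name in advance.

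Part of this stands. The labels do differ, the 20-year version is not fixed in the text, and a direct class-to-class table would need one version throughout. Naming it would be tidy.

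The rest does not carry the point further. The remark about mixed classifications concerns comparison between studies by different groups, not a stated comparison within this cohort. Nothing in the Protocol suggests that different phases would be graded differently; holding to one version across phases is ordinary reading practice. The class definitions are the kind of detail that a reading manual or statistical analysis plan commonly supplies. The argument that prediction of adult shape from the 5-year class requires a common scale is wrong, as the table above shows.

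**Conclusion.** No change to the plan follows. The discrepancy is a missing qualifier in a short list, and the Protocol followed as written still yields a valid grading of hip shape at 20 years on either version. The risk-factor aim is unaffected. The possible harm is confined to a direct table of 5-year against 20-year class, which the Protocol does not propose and which could be put on one scale from the films collected.

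No numerical size can be given, because the Protocol does not say how the two versions differ or whether it intends two versions at all. The conclusion rests on two assumptions: that one version is used consistently for all 20-year films, and that anyone who later tabulates the two time points grades both on the same version. Both are what a competent reading team and analyst would do without being told.

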***Endpoints (primary /secondary)***

Clinical endpoints will be the hip function and quality of life reported by the patients, using the Hip disability and Osteoarthritis Outcome Score (HOOS) (20). There will also be included functional and activity related aspects of a greater population based study in Oslo (21). Furthermore, length leg discrepancies, muscle impairment and Hip impingement tests will be performed.

HOOS: Validated PROM.40 questions to evaluate hip symptoms, hip function on different activity levels and quality of life.

«Oslo population study»: Scientific population study in Oslo to evaluate cardiac risks (21).

If patients would like to participate in the study, but fail to meet up for the visit, a short telephone interview will be performed including a short HOOS\_PS form.

Radiological endpoints

- a.) Stulberg classification
- b.) Coverage of the femoral head (CE angle)
- c.) Osteoarthritis - Jacobsen et al.(22)
- d.) Alterations of the proximal femur (ATD, CCD)
- e.) Total hip replacement.

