## Plan

2018	Identification of all patients
2018 - 2019	Pilotstudy with 20 randomised patients
2019	Dataanalysis og pilot study
2019 - 2020	Phase 1
2020	Data analysis Phase 1
2020 – 2021	Phase 2:
2022	Data analysis
2023	Phase 3:
2023	Data analysis
2023 – 2025	Publication

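### Does it matter that the section headed primary and secondary endpoints never says which endpoint is primary?

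*Protocol*

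**What the plan says.** The Protocol section headed "Endpoints (primary /secondary)" opens with "Clinical endpoints will be the hip function and quality of life reported by the patients", to be measured with the HOOS. It then adds items from an Oslo population study and three examination findings: leg length, muscle function and impingement. A short telephone form of the HOOS serves patients who wish to take part but do not attend. A second list gives five radiological entries: Stulberg class, CE angle, osteoarthritis, shape of the proximal femur (ATD and CCD) and total hip replacement. Neither list, and no single item, is called primary or secondary.

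The other sections do not designate one either. The Background says "This study elucidates the hip function, the residual deformity and the patients reported outcome 20 years after the diagnosis with LCPD". The Purpose section says the aim is to "evaluate long term outcomes, risk factors and patient reported outcomes in young adults". The Significance section says "It elucidates both radiographic and clinical aspects 20 years after the diagnosis".

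The Plan section lists "Dataanalysis og pilot study" for 2019, "Data analysis Phase 1" for 2020, further analyses in 2022 and 2023, and publication in 2023 to 2025.

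**The concern.** A heading that announces a primary/secondary split, followed by text that makes none, looks like an unfinished decision. Choosing the primary endpoint normally belongs in the protocol, so an unseen statistical analysis plan does not fully explain its absence. With more than ten candidate outcomes and four scheduled analyses, the investigators could see results before deciding which outcome to put first. A reader of the final paper could not then check from the Protocol whether the headlined result was the planned one. If each outcome were tested at 5%, the chance that at least one would look significant by luck would be well above 5%.

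**Working it through.** **1. Is any outcome designated?** Setting the sections side by side, the answer is no in the text available. The endpoints section groups by type. The Background, Purpose and Significance sections name several aspects together. Listing the clinical outcomes first does not make them primary.

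**2. Does the text show a preference?** Yes, though it is not a designation.
- The section on unsolved issues criticises earlier work: "The main endpoints of most of the studies are based on radiographs, leaving the functional aspect unrecognized".
- The Significance section presents hip function and patient-reported measures as what earlier long-term studies lacked.
- The endpoints section starts with patient-reported function and quality of life and introduces the other clinical items as additions.

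The outcomes are therefore unlabelled but not all on the same footing.

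**3. How many outcomes?** The count depends on grouping.
- Low: HOOS function, HOOS quality of life, Oslo items, leg length, muscle function and impingement (6), plus five radiological entries: 6 + 5 = 11.
- Central: add HOOS symptoms and count ATD and CCD separately: 11 + 2 = 13.
- High: also count the telephone form and split the Oslo items: 13 + 2 = 15. This is generous, because the telephone form replaces the visit questionnaire and is not an extra endpoint.

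**4. What would the error rate be if each outcome were tested?** The Protocol gives no figure to reproduce. Assume one two-sided 5% test per outcome and no true effect. For k independent outcomes the chance of at least one false positive is 1 − 0.95^k:
- k = 11: 1 − 0.95^11 = 0.431
- k = 13: 1 − 0.95^13 = 0.487
- k = 15: 1 − 0.95^15 = 0.537

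For equally correlated normal statistics, with rejection when |z| > 1.96 and numerical integration over the shared component, k = 13 gives 0.334 at correlation 0.5 and 0.192 at correlation 0.8.

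**5. Do these figures apply here?** No. A false positive needs a null hypothesis and a contrast, and the Protocol states neither. A Stulberg distribution, a mean CE angle or a hip replacement rate at 20 years is an estimate, not a test. Risk-factor analyses, which the Purpose section mentions, would involve contrasts. None is specified, however, and their form is usually left to the analysis plan. The 19% to 49% range for k = 13 describes an analysis that the document does not contain.

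**6. How much could early analyses reveal?** The pilot has 20 patients out of 425, or 20/425 = 4.7%. The phase sections list 208 + 187 + 27 = 422 patients. Even an outcome named only after the Phase 1 analysis would be fixed in advance for 187 + 27 = 214 of these, or 214/422 = 51%. If all 20 pilot patients came from Phases 2 and 3, which the Protocol does not say, 214 − 20 = 194 would remain.

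**The case for a change.** The strongest case for a change is that the Protocol opened a section to make this decision and did not make it. It faults earlier studies for their choice of main endpoint, so it accepts that the choice matters. It also expects its results to influence future treatment. Selective emphasis is possible in a descriptive cohort too, without any significance test. Naming one HOOS function score as primary would cost a line of text.

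Part of this stands. The heading and the text do not match, and the available text does not tell a reader which result is the main one. Reading the clinical group as primary would not settle the matter, since that group holds several outcomes and the HOOS itself covers more than one domain.

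The rest does not carry a change. Nothing in the Protocol says that an outcome will be selected after seeing data, or that confirmatory claims will be made phase by phase. Analysing each regional block as it completes is not a fault. Rules on pooling, and on the standing of the earlier analyses, are commonly left to a statistical analysis plan, which may exist. The choice of primary would remain the investigators' own, so the request is to write down a label, not to correct a rule that gives a wrong answer.

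**Conclusion.** The observation is correct, but it is a gap that analysts can fill sensibly, and it needs no change to the plan. If every listed outcome is reported descriptively for the cohort, as the text implies, the results are sound whichever one is called primary. No stated rule produces a wrong estimate or conclusion, and no test level is there to be inflated.

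The size is qualitative: some uncertainty about which result leads. No false-positive rate should be attached to it. The authors can limit the uncertainty in the report by showing all listed outcomes and saying when the lead outcome was chosen.

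This conclusion rests on two assumptions: the study remains a descriptive follow-up with no confirmatory hypothesis, and the front pages not available here do not state otherwise. If the investigators meant to base a formal claim on a significance test of one outcome, that outcome would have to be fixed before the data were analysed.

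### Willing patients who miss the visit are assigned only a short HOOS_PS by telephone, although the full HOOS that carries the quality-of-life endpoint does not need attendance (cheap improvement, low priority)

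*Protocol*

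**What the plan says.** The Endpoints section of the protocol opens with "Clinical endpoints will be the hip function and quality of life reported by the patients" and gives HOOS as the instrument. It describes HOOS as a validated measure with 40 "questions to evaluate hip symptoms, hip function on different activity levels and quality of life". The list of radiological endpoints in the same section ends with "e.) Total hip replacement".

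For people who are willing but do not attend, the section provides a fallback: "If patients would like to participate in the study, but fail to meet up for the visit, a short telephone interview will be performed". The sentence goes on to say that the interview includes a short HOOS_PS form. No other content is named.

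The visit is described at the end of the Phase 3 section: "The examination will comprise a clinical visit with functional testing of the hip and radiographs of both hips". HOOS is not listed there, and the protocol nowhere says how or when the full HOOS is given. Under Material and methods the intention is full coverage: "The study will follow up all 425 patients".

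**The concern.** Patient-reported outcome is central to this study. The Background says "This study elucidates the hip function, the residual deformity and the patients reported outcome 20 years after the diagnosis with LCPD", and the Purpose is "to evaluate long term outcomes, risk factors and patient reported outcomes in young adults, 20 years after LCPD". The Significance section presents the use of patient-reported measures as part of what is new.

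Radiographs, leg-length measurement and impingement tests need the patient in the clinic. A questionnaire that the patient answers does not. The patients covered by the fallback have agreed to take part and are already on the telephone, so they are the easiest source of further data on the clinical endpoints. The protocol nevertheless names only a reduced form for them.

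What is at stake is the completeness of the quality-of-life endpoint in this group. This is a choice about data collection, and an analysis plan cannot recover answers that were never asked for. Total hip replacement is a lesser matter. A patient can report it by telephone, but no such question is named.

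**Working it through.** The protocol gives no attendance figure, telephone-only share, standard deviation or precision target, so there is no figure of its own to reproduce. The check has two parts.

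**1. What is named for whom**

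| Item | Attenders | Willing non-attenders |
|---|---|---|
| Hip function, patient-reported | HOOS | HOOS_PS by telephone |
| Quality of life, patient-reported | HOOS | nothing named, unless the HOOS_PS covers it (content not described) |
| Total hip replacement | listed with the radiological endpoints | nothing named |

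The column for attenders assumes that the full HOOS is given in connection with the visit. The existence of a separate fallback suggests this but does not establish it.

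**2. Possible size**

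Inputs:
- N = 425, the cohort in Material and methods. Using it as the number taking part is an upper limit.
- p = share of participants reached by telephone only. It is assumed to be 5%, 10%, 20% or 30%.
- c = share of those patients who complete the full HOOS when offered it. It is assumed to be 50%, or 100% as an upper limit.

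Patients affected = 425 × p.

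Without the offer, the quality-of-life score is available for N(1 − p) patients. With it, the score is available for N(1 − p + pc). A standard error varies as one over the square root of the number of patients. With equal variance in both groups, the standard error without the offer relative to that with it is therefore

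ratio = √[(1 − p + pc) / (1 − p)],

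and N cancels. For p = 0.20 and c = 0.5 this is √(0.90 / 0.80) = √1.125 = 1.061.

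| p | 425 × p | Ratio, c = 0.5 | Ratio, c = 1 |
|---|---|---|---|
| 0.05 | 21.25 (about 21) | √(0.975/0.95) = 1.013 | √(1/0.95) = 1.026 |
| 0.10 | 42.5 (about 43) | √(0.95/0.90) = 1.027 | √(1/0.90) = 1.054 |
| 0.20 | 85 | √(0.90/0.80) = 1.061 | √(1/0.80) = 1.118 |
| 0.30 | 127.5 (about 128) | √(0.85/0.70) = 1.102 | √(1/0.70) = 1.195 |

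These ratios hold only if the full HOOS is given at the visit alone and the HOOS_PS has no quality-of-life items. If either condition fails, the ratio is nearer to 1. At shares of 5% to 10% the gain is small, especially if only half respond.

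**The case against.** The strongest reply is that nothing in the text is wrong. A smaller dataset for people who cannot attend does not conflict with a fuller one for those who do, and a short interview can be a deliberate trade of depth for response. That stands: this is an improvement to a choice already made, and the protocol does not contradict itself here. It does not defeat the point, because the proposal leaves the short form in place and first in order, so the planned data do not depend on the longer form.

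Three stronger readings are tempting, and the protocol does not support them.

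- A reader might infer that quality of life will certainly be missing for non-attenders. That needs two facts the protocol does not state: that the full HOOS is tied to the visit, and that the HOOS_PS omits quality of life.
- A reader might infer that hip replacements among non-attenders will go unrecorded. The interview is described as including the short form, which leaves room for other questions, and such detail may sit in an interview guide. The finding is only that no such question is named. Hip replacement is also filed under the radiological endpoints, so a telephone answer is not the same measurement without confirmation.
- A reader might infer that the results will be biased. The protocol gives nothing on how non-attenders differ from attenders or how many there will be, so no bias can be shown or sized.

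It is also fair to say that no stated precision or power target is missed, and that both shares in the calculation are assumptions.

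**Conclusion.** The point holds as a cheap improvement of low priority. The only instrument the protocol names for willing non-attenders is shorter than the one that defines its clinical endpoints, although the full questionnaire does not require attendance.

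The loss is conditional on the two unstated premises about the full HOOS and the short form. If both are true, the standard error of the mean quality-of-life score would be about 1.01 to 1.10 times what it could be if half of the telephone-only patients completed the full form, and at most 1.03 to 1.20 times if all did, over assumed telephone-only shares of 5% to 30%. The case rests on small cost and on the fact that uncollected answers cannot be recovered. It does not rest on a demonstrated error. The hip replacement question is a useful addition to the same call and would not be enough to raise the point by itself.

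**What to change.** In the Endpoints section:

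1. Keep the HOOS_PS in the telephone interview and complete it first.
2. Then offer every willing non-attender the full HOOS by post, online or telephone.
3. Record the mode of collection for each patient.
4. In the same call, ask about total hip replacement (yes or no, side, date). Report the answer as self-reported unless it is confirmed from records or radiographs.

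If the full HOOS already goes to all participants whether or not they attend, one sentence saying so is enough in place of step 2; step 3 still applies, and only the hip replacement question then needs adding.

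The cost is a few more minutes on the telephone or postage per patient. Some patients will not return the longer form. Answers may also differ by mode of collection; recording the mode makes this visible but does not remove it.

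### Does listing total hip replacement beside the other radiological endpoints hide the worst hips and understate osteoarthritis and deformity?

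*Protocol*

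**What the plan says.** Under Endpoints (primary /secondary), the protocol gives a lettered list of radiological endpoints. It opens with "a.) Stulberg classification", goes on to femoral head coverage by CE angle, osteoarthritis graded by a published method, and the proximal femur measurements ATD and CCD, and closes with "e.) Total hip replacement". The items are not ranked, and nothing is said about how one bears on another.

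Three other statements matter:

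- Purpose of the study: the aim covers long-term outcomes, "risk factors and patient reported outcomes in young adults, 20 years after LCPD".
- Material and methods: "The study will follow up all 425 patients and it is structured in 3 phases". The Phase 3 section adds that everyone is invited to an examination with films of both hips. It also records that films from diagnosis, 1 year and 5 years were collected, with a modified Stulberg class at 5 years.
- Background, on residual deformity: "Such a hip may also predispose for early hip osteoarthritis".

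The protocol does not say that a replaced hip is excluded, set to missing or removed from any denominator.

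**The concern.** The five items look parallel but are not. Items a to d need a native femoral head, joint or proximal femur, and item e removes it. By the protocol's own account, deformity may lead on to early osteoarthritis. If replacement was done for a failed Perthes hip, that hip sits at the far end of what a to d are meant to measure.

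Reading a to d only in hips that still have a native joint would then condition on not having failed. Osteoarthritis prevalence and the share of severe Stulberg classes would look better than they are. Associations with risk factors might be diluted, and a good HOOS in a patient with a prosthesis might be taken for a good natural outcome. In a study whose purpose is long-term outcome and its risk factors, that would matter.

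**Working it through.** **Inputs.** From the protocol: 425 patients (Material and methods). Not in the protocol, so assumed: the replaced share t, the osteoarthritis prevalence p in native hips, one affected hip per patient, full attendance, and every replacement done for the Perthes hip. The protocol states no rate of its own to reproduce.

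**Step 1: the gap if replaced hips are left out.** Prevalence in native hips is p. Counting each replaced hip as end-stage gives t + (1 − t)p. The difference is t(1 − p).

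With p = 20%:

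- t = 2%: 0.02 + 0.98 × 0.20 = 21.6%, a gap of 1.6 points
- t = 5%: 0.05 + 0.95 × 0.20 = 24.0%, a gap of 4.0 points
- t = 10%: 0.10 + 0.90 × 0.20 = 28.0%, a gap of 8.0 points

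**Step 2: a wider range, set against sampling error.** The standard error (SE) of the native-hip prevalence is √[p(1 − p) / (425(1 − t))].

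| t (hips) | p | t + (1 − t)p | Gap, points | SE, points |
|---|---|---|---|---|
| 1% (about 4) | 5% | 5.95% | 0.95 | 1.06 |
| 1% | 15% | 15.85% | 0.85 | 1.74 |
| 1% | 30% | 30.70% | 0.70 | 2.23 |
| 5% (about 21) | 5% | 9.75% | 4.75 | 1.08 |
| 5% | 15% | 19.25% | 4.25 | 1.78 |
| 5% | 30% | 33.50% | 3.50 | 2.28 |
| 10% (about 43) | 5% | 14.50% | 9.50 | 1.11 |
| 10% | 15% | 23.50% | 8.50 | 1.83 |
| 10% | 30% | 37.00% | 7.00 | 2.34 |

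At 1% the gap is below one standard error throughout; at 5% and 10% it is above. The direction is certain, but the size rests on a rate that the protocol does not give.

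**Step 3: what is lost when both endpoints are reported.** Take t = 5% and p = 15%. Item e reports 0.05 × 425 = 21.25 replacements (expected number). Item c reports 0.15 × 403.75 = 60.56 osteoarthritic native hips. Together that is 81.81 / 425 = 19.25%, exactly the combined figure in the table. The 15% and the 19.25% answer different questions. The first misleads only if it is presented as the figure for all 425 with the replacements unmentioned, and the endpoint list calls for the replacements to be reported.

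**Step 4: the other endpoints.** For "b.) Coverage of the femoral head (CE angle") and "d.) Alterations of the proximal femur (ATD, CCD") no gap can be computed: they are continuous measurements, and the protocol gives no distribution and no worst direction. For shape, the 5-year Stulberg class is a recorded fallback in replaced hips. HOOS can still be collected after replacement, and the protocol defines no good or poor category into which such a patient could be misplaced. It specifies no model for risk factors, so a diluted association is possible but cannot be shown.

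**The case for a change.** The strongest argument for a change is that what an endpoint means in a hip where it cannot be read belongs to its definition and also governs data collection. The protocol mentions neither the date of replacement nor retrieval of films taken before it. If these are not gathered, a later SAP could not supply a last native reading or a time-to-replacement analysis. The 5-year Stulberg class says nothing about osteoarthritis arising afterwards. Time at risk also varies: diagnoses fall in 1996–2000 and visits run from 2019 to 2023, so follow-up spans about 19 (2019 − 2000) to 27 (2023 − 1996) years.

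Part of this stands. The linking rule is indeed absent, and a careful team would note the operation date and identify replaced hips beside the HOOS results. But counting osteoarthritis or replacement together needs neither the date nor an earlier film, only items c and e, both of which are to be collected. The time-to-event analysis and the last pre-operative reading are additions that the stated aims do not require. HOOS with a prosthesis in place is a legitimate patient-reported outcome 20 years on; preferring another target is a choice, not a correction.

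**Conclusion.** The concern does not call for a change. It is true that Stulberg class, CE angle, osteoarthritis grade, ATD and CCD cannot be read in a replaced hip at the visit, and that no rule covers this. It is not shown that such hips drop out or that severity is understated: the protocol never excludes them, and listing replacement separately keeps them in view. The possible understatement of osteoarthritis or worse is t(1 − p), from under 1 point at an assumed 1% replaced to 7.0–9.5 points at an assumed 10%. It is zero once replaced hips are counted as end-stage or the two endpoints are read together. The choice among worst category, combined outcome or last earlier film is an analysis rule commonly set in the SAP, and analysts can fill it sensibly from what is collected. This conclusion assumes that osteoarthritis and replacement are both reported with their denominators, as the endpoint list implies.
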